#### **13.4.2 Second Secondary Efficacy Analysis**

The preceding estimated mean change from baseline in A4 is conducted on the log scale due to the inherent skewness and non-Normality of untransformed A4 values. While back transformation of log scale analysis results leads to interpretable quantities on the ratio scale, interest still resides in appreciation of the results on the absolute scale in ng/dL units.

Given the non-Normality of A4 values, a simplistic analysis of  $CFB = (\text{Week 18 A4 value} - \text{baseline A4 value})$  is inappropriate as this simple CFB will also be non-Normal, resulting in upwardly biased estimates of mean A4 level and inflated SDs and SEs; consequently power will also be eroded.

Thus, to address the Second Secondary Efficacy Analysis (see [Table 1](#), Analysis 2.2) and facilitate the presentation of results on both the ratio (i.e. % change) and absolute scales, the Primary Analysis repeated measures random coefficients mixed-effects model will be re-run exactly as described in [Section 13.3.3](#) but with log A4 as the dependent variable as opposed to the change (i.e. as opposed to log A4 value minus log baseline value). Note, this re-run of the model with log A4 as the dependent variable will give precisely the same results, parameter estimates and variance-covariance matrix estimate as the analysis with log A4 minus log baseline as the dependent variable.

As described with example SAS codes in Appendix E, the delta theorem will be applied to the log scale results to provide consistent estimates of the CFB in A4 values on the absolute scale

together with an estimate for the difference in LSmeans and the associated 95% CI. Results will be presented for the absolute change in A4 at 4, 8 and 12 weeks of double blind randomized treatment. A serial plot will be presented of the estimated absolute mean change from baseline in log A4 over time. The y-axis will be the CFB in ng/dL and the x-axis will display baseline, week 4, week 8 and week 12 of double blind randomized treatment. All treatment groups will be presented on the graph.

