**Table 1 Study 203 Objectives and Endpoints**

Objective	Efficacy Analysis	
Primary Efficacy		
To evaluate the effect of tildacerfont in reducing A4 in subjects with classic CAH over 12 weeks	1.1.	Assessment of dose response for change from baseline in log A4 after 12 weeks on double-blind, placebo-controlled treatment (Week 18)
Secondary Efficacy		
To evaluate the effect of tildacerfont in reducing A4 in subjects with classic CAH over 12 weeks	2.1.	Change from baseline in A4 as assessed on the log scale after 12 weeks on double-blind, placebo-controlled treatment (Week 18)
To evaluate the effect of tildacerfont in reducing A4 in subjects with classic CAH over 12 weeks	2.2.	Absolute change from baseline in A4 as determined via application of the delta theorem to the log scale analysis results after 12 weeks on double-blind, placebo-controlled treatment (Week 18)

Objective	Efficacy Analysis	
To evaluate the effect of tildacerfont in reducing 17-OHP in subjects with classic CAH over 12 weeks	2.3.	Assessment of dose response for change from baseline in log 17-OHP after 12 weeks on double-blind, placebo-controlled treatment (Week 18)
To evaluate the effect of tildacerfont in reducing 17-OHP in subjects with classic CAH over 12 weeks	2.4.	Change from baseline in 17-OHP as assessed on the log scale after 12 weeks on double-blind, placebo-controlled treatment (Week 18)
To evaluate the effect of tildacerfont in reducing 17-OHP in subjects with classic CAH over 12 weeks	2.5.	Absolute change from baseline in 17-OHP as determined via application of the delta theorem to the log scale analysis results after 12 weeks on double-blind, placebo-controlled treatment (Week 18)
Exploratory Efficacy		
To evaluate the effect of tildacerfont in reducing A4 in subjects with classic CAH over 12 weeks	3.1.	Proportion of subjects who achieve adequate control of A4 (A4 $\leq$ 1x, 1.25x, 1.5x, 1.75x and 2x ULN) after 12 weeks on double-blind, placebo-controlled treatment (Week 18) for each treatment group
To evaluate the effect of tildacerfont in reducing 17-OHP in subjects with classic CAH over 12 weeks	3.2.	Proportion of subjects who achieve adequate control of 17-OHP (17-OHP $\leq$ 1200 ng/dL) after 12 weeks on double-blind, placebo-controlled treatment (Week 18) for each treatment group

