#### **13.4.5 Fifth Secondary Endpoint Analysis**

To address the Fifth Secondary Efficacy Analysis regarding the change from baseline in 17-OHP on the absolute scale (see [Table 1](#), Analysis 2.5), the analysis and presentation of results will be conducted in exact concordance with the Third Efficacy Analysis of A4 as described in

[Section 13.4.2](#) with the only difference being the removal of log A4 as a covariate and the inclusion of the randomization stratification variable (study Week 4 A4 value [0 =  $A4 \leq 4 \times ULN$ ; 1 =  $A4 > 4 \times ULN$ ]) as a fixed factor effect.

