## 21 Appendix E: Calculating Absolute CFB and Absolute Treatment Effects for A4 at Based on Analyses Conducted on the Log Scale.

The A4 Primary Efficacy Analysis is conducted on the log scale due to the inherent skewness and non-Normality of untransformed A4 values. While back transformation of log scale analysis results leads to interpretable quantities on the ratio scale, interest still resides in appreciation of the results on the absolute scale in ng/dL units. Given the non-Normality of A4 values, a simplistic analysis of  $CFB = (\text{Week 18 A4 value} - \text{baseline A4 value})$  is inappropriate as this simple CFB will also be non-Normal, resulting in upwardly biased estimates of mean A4 level and inflated SDs and SEs.

Thus, to address the Second Secondary Efficacy Analysis ([Table 1](#), Analysis 2.2), the Primary Analysis repeated measures random coefficients mixed-effects model will be re-run exactly as described in [Section 13.3.3](#) but with log A4 as the dependent variable as opposed to the change (i.e. as opposed to log A4 value minus log baseline value). Note, this re-run of the model with log A4 as the dependent variable will give precisely the same results, parameter estimates and variance-covariance matrix estimate as the analysis with log A4 minus log baseline as the dependent variable. The resulting estimates of mean log A4 and mean change from baseline in log A4 will be used via the Delta Theorem to provide consistent estimate of A4 treatment effects on the absolute scale.

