### Delta Theorem

Suppose  $x_{ij}$  are independent, identically distributed Normal random variables with  $i = E$  and  $C$  representing experimental and control treatments, and  $j = 1 \dots n_i$  representing subject number. Then  $x_{ij} \sim N(\mu_i, \sigma^2)$  and  $\bar{x}_i \sim N(\mu_i, \sigma^2/n_i)$ .

Suppose there is interest in the function of  $\bar{x}_i$ , i.e.,  $u_i = f(\bar{x}_i)$ . Then, the delta theorem (= first order Taylors expansion of  $u_i$ ) as described by Armitage et al ([Armitage 2010](#)) states that the variance of  $u_i$  is given by

$$Var(u_i) = \left[ \frac{\partial f}{\partial \bar{x}_i} \right]^2 Var(\bar{x}_i)$$

And, further,

$$Var(u_E - u_C) = \left[ \frac{\partial f}{\partial \bar{x}_E} \right]^2 Var(\bar{x}_E) + \left[ \frac{\partial f}{\partial \bar{x}_C} \right]^2 Var(\bar{x}_C) + 2 \left[ \frac{\partial f}{\partial \bar{x}_E} \right] \left[ \frac{\partial f}{\partial \bar{x}_C} \right] Cov(\bar{x}_E, \bar{x}_C)$$

In the case of the Primary Efficacy Analysis, let  $\bar{x}_i$  represent the estimated A4 CFB on the log scale,  $L_i$ , with  $Var(L_i) = [SE(\bar{x}_i)]^2$  and  $Cov(L_E, L_C) = Cov(\bar{x}_E, \bar{x}_C)$  where  $Cov(\dots)$  denotes covariance.

Interest lies in A4 on the absolute scale, i.e. in the function  $f(y) = e^{-y}$ , and thus in the function  $u_i = e^{-L_i}$ . Hence,

$$Var(u_i) = [-e^{-L_i}]^2 Var(L_i) = e^{-2L_i} \cdot Var(L_i)$$

and

$$Var(u_E - u_C) = e^{-2L_E} \cdot Var(L_E) + e^{-2L_C} \cdot Var(L_C) + 2 Cov(L_E, L_C) \cdot e^{-L_E} \cdot e^{-L_C}$$

Hence, the estimate of the absolute difference in mean A4 values,  $E - C$ , is given by

$u_E - u_C = e^{-L_E} - e^{-L_C}$  with  $SE(u_E - u_C) = \sqrt{Var(u_E - u_C)}$  such that the  $100(1 - \alpha)\%$  CI is given by

$$(u_E - u_C) \pm t_{df, \alpha/2} \cdot \sqrt{Var(u_E - u_C)}$$

where  $t_{df, \alpha/2}$  represents the  $(1 - \alpha/2)$  percentile of the studentized  $t$  cumulative distribution function on  $df$ , where  $df$  is the error degrees of freedom associated with the corresponding log scale A4 treatment effect estimate at 18 Weeks from the Primary Efficacy Analysis model.

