## Example SAS Code

The following SAS codes provides an illustrative application of the Delta Theorem.

```
OPTIONS PAGESIZE=58 LINESIZE=180 NONUMBER NODATE;

** DEPENDENT VARIABLE IS LOG PULSE ** ;
PROC MIXED DATA=STUDY2 COVTEST NOCLPRINT METHOD=ML;
  CLASS ID G T;
  MODEL LPULSE = LBASE T G T*G / SOLUTION OUTP=PRED1R OUTPM = PRED1F;
  REPEATED T / TYPE=UN SUBJECT = ID;
  LSMEANS T*G / PDIFF DIFF ALPHA=0.05 CL COV;
  ODS OUTPUT LSMEANS=LSM;
  ODS OUTPUT DIFFS=LSMDIFF;
  TITLE 'LOG ABS MMRM';
  RUN;
  TITLE;

*** TRT EFFECT BASE ON ABSOLUTE SCALE **;
%MACRO ABSTRTEFF(DRUG,PCBO,T,CVPOS,DAT);
DATA DRUG;
  SET LSM;
  LENGTH LABEL $12.;
  LABEL=LEFT(TRIM(PUT(&DRUG,1.0)))||' V '||LEFT(TRIM(PUT(&PCBO,1.0)));
  IF T=&T AND G=&DRUG;
  CV=COV&CVPOS;
  TIME=&T;
  DRUG=ESTIMATE;
  SEDRUG=STDERR;
  DF=DF;
  KEEP LABEL TIME DF DRUG SEDRUG CV;
RUN;
DATA PCBO;
  SET LSM;
  LENGTH LABEL $12.;
  LABEL=LEFT(TRIM(PUT(&DRUG,1.0)))||' V '||LEFT(TRIM(PUT(&PCBO,1.0)));
  IF T=&T AND G=&PCBO;
  TIME=&T;
  PCBO=ESTIMATE;
  SEPCBO=STDERR;
  KEEP LABEL TIME PCBO SEPCBO;
RUN;
PROC SORT DATA = DRUG;BY LABEL TIME;RUN;
PROC SORT DATA = PCBO;BY LABEL TIME;RUN;
DATA COMB&DAT;
  MERGE DRUG PCBO;
  BY LABEL TIME;
  ABSDRUG=EXP(DRUG);
  ABSPCBO=EXP(PCBO);
  ABSEFF= ABSDRUG-ABSPCBO;
  ABSDRUGV= SEDRUG**2*ABSDRUG**2;
  ABSPCOV= SEPCBO**2*ABSPCBO**2;
  V = SEDRUG**2*ABSDRUG**2 + SEPCBO**2*ABSPCBO**2 - 2*CV*ABSDRUG*ABSPCBO;
  ABSLOWER = ABSDRUG-ABSPCBO - SQRT(V)*QUANTILE('T',0.975,DF);
  ABSUPPER = ABSDRUG-ABSPCBO + SQRT(V)*QUANTILE('T',0.975,DF);
  ABSP = 2*(1-CDF('T',ABS(ABSDRUG-ABSPCBO)/SQRT(V),DF));
RUN;
```

```
%MEND ABSTRTEFF;

%ABSTRTEFF(1,3,1,7,1);
%ABSTRTEFF(1,3,2,7,2);
%ABSTRTEFF(1,3,3,7,3);
%ABSTRTEFF(2,3,1,7,4);
%ABSTRTEFF(2,3,2,7,5);
%ABSTRTEFF(2,3,3,7,6);

DATA COMB;
  SET COMB1 COMB2 COMB3 COMB4 COMB5 COMB6;
RUN;

PROC PRINT DATA = COMB;
  TITLE 'TREATMENT EFFECT ON ABSOLUTE SCALE';
RUN;
TITLE;

** DEPENDENT VARIABLE IS NOW LOG CHANGE = LOG PULSE - LOG BASE ** ;
PROC MIXED DATA=STUDY2 COVTEST NOCLPRINT METHOD=ML;
  CLASS ID G T;
  MODEL LCFB = LBASE T G T*G / SOLUTION OUTP=PRED1R OUTPM = PRED1F;
  REPEATED T / TYPE=UN SUBJECT = ID;
  LSMEANS T*G / PDIFF DIFF ALPHA=0.05 CL COV;
  ODS OUTPUT LSMEANS=LSM_;
  ODS OUTPUT DIFFS=LSMDIFF_;
  TITLE 'LOG CFB MMRM';
RUN;
TITLE;

DATA LSMDIFF_;
  SET LSMDIFF_;
  IF T = _T AND G NE _G ;
  IF _G=3;
  TIME=T;
  LABEL=LEFT(TRIM(PUT(G,1.0)))||' V '||LEFT(TRIM(PUT(_G,1.0)));
  KEEP ESTIMATE STDERR LOWER UPPER PROBT TIME LABEL;
RUN;

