*** TRT EFFECT ON LOG SCALE **;
%MACRO ABSTRTEFF2(DRUG,PCBO,T,DAT);
DATA DRUG;
  SET LSM_;
  LENGTH LABEL $12.;
  LABEL=LEFT(TRIM(PUT(&DRUG,1.0)))||' V '||LEFT(TRIM(PUT(&PCBO,1.0)));
  IF T=&T AND G=&DRUG;
  TIME=&T;
  DRUG _ESTIMATE;
  KEEP LABEL TIME DRUG_;
RUN;
DATA PCBO;
  SET LSM_;
  LENGTH LABEL $12.;
  LABEL=LEFT(TRIM(PUT(&DRUG,1.0)))||' V '||LEFT(TRIM(PUT(&PCBO,1.0)));
  IF T=&T AND G=&PCBO;
  TIME=&T;
  PCBO _ESTIMATE;
  KEEP LABEL TIME PCBO_;
RUN;
PROC SORT DATA = DRUG;BY LABEL TIME;RUN;
PROC SORT DATA = PCBO;BY LABEL TIME;RUN;
```

```
DATA COMB_&DAT;
MERGE DRUG PCBO;
BY LABEL TIME;
RUN;

%MEND ABSTRTEFF2;

%ABSTRTEFF2 (1,3,1,1);
%ABSTRTEFF2 (1,3,2,2);
%ABSTRTEFF2 (1,3,3,3);
%ABSTRTEFF2 (2,3,1,4);
%ABSTRTEFF2 (2,3,2,5);
%ABSTRTEFF2 (2,3,3,6);

DATA COMB_;
SET COMB_1 COMB_2 COMB_3 COMB_4 COMB_5 COMB_6;
RUN;

PROC PRINT DATA = COMB_;
TITLE 'TREATMENT EFFECT ON LOG SCALE';
RUN;
TITLE;

PROC SORT DATA = COMB;BY LABEL TIME;RUN;
PROC SORT DATA = COMB_;BY LABEL TIME;RUN;
PROC SORT DATA = LSMDIFF_;BY LABEL TIME;RUN;

DATA ALL;
MERGE COMB COMB_ LSMDIFF_;
BY LABEL TIME;
BASED = DRUG - DRUG_;
BASEP = PCBO - PCBO_;
BASEC = LEFT(TRIM(PUT(ROUND(EXP(BASED),0.1),5.1)));
DRUGC = LEFT(TRIM(PUT(ROUND(EXP(DRUG ),0.1),5.1)))||'|';
'||LEFT(TRIM(PUT(ROUND(SQRT(ABSDRUGV),0.01),6.2)))||'|';
PCBOC = LEFT(TRIM(PUT(ROUND(EXP(PCBO ),0.1),5.1)))||'|';
'||LEFT(TRIM(PUT(ROUND(SQRT(ABSPCBOV),0.01),6.2)))||'|';
PCTCHGDRUG = LEFT(TRIM(PUT(ROUND(100*(EXP(DRUG_)-1),0.1),6.1)))||'|';
'||LEFT(TRIM(PUT(ROUND(0.0001),6.4)))||'|';
PCTCHGPCBO = LEFT(TRIM(PUT(ROUND(100*(EXP(PCBO_)-1),0.1),6.1)))||'|';
'||LEFT(TRIM(PUT(ROUND(SEPCBO,0.0001),6.4)))||'|';
EFFECTPCTCHG = LEFT(TRIM(PUT(ROUND(100*(EXP(ESTIMATE)-1),0.1),6.1)))||'|';
'||LEFT(TRIM(PUT(ROUND(100*(EXP(LOWER)-1),0.1),6.1)));
||'|', '||LEFT(TRIM(PUT(ROUND(100*(EXP(UPPER)-1),0.1),6.1)))||'|';
EFFECTABSCHG = LEFT(TRIM(PUT(ROUND(ABSEFF,0.1),6.1)))||'|';
'||LEFT(TRIM(PUT(ROUND(ABSLOWER,0.1),6.1)));
||'|', '||LEFT(TRIM(PUT(ROUND(ABSUPPER,0.1),6.1)))||'|';
P_LOGEFFECT = PUT(PROBT,PVALUE7.4);
P_ABSEFFECT = PUT(ABSP,PVALUE7.4);
RUN;

PROC SORT DATA = ALL;BY LABEL TIME;RUN;
PROC PRINT DATA = ALL SPLIT='*' ;
BY LABEL;
ID LABEL;
LABEL TIME= 'TIME*POINT'
LABEL= 'TRT*COMP'
BASEC= 'BASELINE*(BPM)'
DRUGC= 'DRUG ABS*MEAN [SE]*(BPM)'
PCBOC= 'PCBO ABS*MEAN [SE]*(BPM)'
PCTCHGDRUG = 'DRUG PCT CFB*MEAN [SE]'
```

```
PCTCHGPCBO = 'PCBO PCT CFB*MEAN [SE]'  
EFFECTPCTCHG= 'DRUG-PCBO PCT EFFECT*(95 %CI)'  

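### Secondary analyses 2.2 and 2.5 estimate differences in geometric means but are described as consistent estimates of mean change in ng/dL

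*SAP*

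**What the plan says.** SAP Table 1 defines analysis 2.2 as "Absolute change from baseline in A4 as determined via application of the delta theorem to the log scale analysis results" at Week 18. Section 13.4.5 applies the same method to analysis 2.5, "regarding the change from baseline in 17-OHP on the absolute scale". Section 13.4.2 re-runs the primary model with log A4 as the outcome. It says the delta theorem is then "applied to the log scale results to provide consistent estimates of the CFB in A4 values on the absolute scale".

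Appendix E calls the resulting contrast "the estimate of the absolute difference in mean A4 values". In the example code the drug-arm line begins "ABSDRUG=EXP(DRUG", where DRUG is the log-scale least squares mean. Placebo is treated the same way, and the effect is "ABSEFF= ABSDRUG-ABSPCBO". The output heading begins "DRUGC= 'DRUG ABS*MEAN [SE]*(BPM" (the example data are pulse rates).

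Both 13.4.2 and Appendix E reject a raw change from baseline on the ground that skewness makes it non-Normal, "resulting in upwardly biased estimates of mean A4 level and inflated SDs and SEs".

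Section 13.4.1, on analysis 2.1, describes its back-transformed log-scale results as geometric means and geometric mean ratios. That word does not appear in 13.4.2, 13.4.5 or Appendix E.

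**The concern.** Exponentiating a mean of logs gives a geometric mean, which is the median if the values are log-normal. The delta step adds a standard error but does not change what is being estimated. No σ²/2 or smearing term appears in the text or the code. The quantity computed is therefore not the difference in means that Appendix E names, and more data will not bring the two together.

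The reason given for avoiding the raw scale is also wrong. A sample mean is unbiased for the population mean however skewed the data are. The sentence makes sense only if the target is already the geometric mean or the median.

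Two of the five secondary analyses are affected, and they supply the ng/dL effect sizes that readers are likely to quote. Section 13.3.4 puts arithmetic means and mean changes for A4 in the same report. A model-based figure also labelled a mean would then appear beside an arithmetic mean without a statement that the two have different targets. If log variance differs between arms, the two scales could even rank the doses differently.

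**Working it through.** **Inputs.** The documents give no figure for the absolute-change analyses and no SD for log A4 or log 17-OHP. The log SDs below are assumptions. The only planning variability is in Protocol 9.2: a common SD of 30 percentage points and 15 evaluable subjects per group. The sample size reproduces: 15/0.85 = 17.6, rounded up to 18, and 4 × 18 = 72. The appendix prose uses e^(−L) where the code uses exp of the log mean, so the check follows the code.

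**Formula.** For log-normal values with log mean μ and log SD σ, the geometric mean is exp(μ) and the arithmetic mean is exp(μ + σ²/2). With the same σ in both arms:

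arithmetic difference = exp(σ²/2) × geometric difference.

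Here σ² is the total log variance at the visit, including the spread in baseline.

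**Common log variance, as Appendix E assumes.** The last column takes geometric means of 800 on placebo and 400 on drug, chosen for illustration (reported difference −400 ng/dL).

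| Assumed log SD | exp(σ²/2) | Reported figure too small by | Mean difference (ng/dL) |
|---|---|---|---|
| 0.3 | 1.05 | 4% | −418 |
| 0.5 | 1.13 | 12% | −453 |
| 0.8 | 1.38 | 27% | −551 |
| 1.0 | 1.65 | 39% | −659 |

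**Simulation of the Appendix E steps.** The log value was regressed on log baseline and arm, the adjusted means were exponentiated, and the difference was taken. The assumptions were a geometric-mean baseline of 800, a drug/placebo ratio of 0.7, a baseline log SD of 0.7 and a residual log SD of 0.5.
- True geometric difference: 800 × (0.7 − 1) = −240.
- True mean difference: −240 × exp((0.49 + 0.25)/2) = −347.
- Appendix E estimate in a very large sample: −240, which is the geometric difference.

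**Unequal log variance.** Keep placebo as above and raise the drug-arm residual SD to 0.9.
- Placebo mean: 800 × exp(0.37) = 1158.
- Drug mean: 560 × exp((0.49 + 0.81)/2) = 1073.
- Mean difference: about −85. The Appendix E estimate is still −240, so it overstates the mean reduction.

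For a halving of the geometric mean, understatement turns into overstatement once the drug-arm log SD exceeds 0.69, 1.06 or 1.29, against placebo log SDs of 0.5, 0.8 or 1.0.

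**The protocol's planning SD.** Take the ratio to baseline as log-normal with SD 0.30 in both arms and assumed means of 1.0 on placebo and 0.5 on drug. The geometric mean of such a ratio is m/√(1 + (0.30/m)²).
- Placebo: 1/√1.09 = 0.958. Drug: 0.5/√1.36 = 0.429.
- At a fixed baseline the geometric difference is 0.529 × baseline and the mean difference is 0.500 × baseline, a slight overstatement.
- With baseline spread it becomes an understatement once the baseline log SD exceeds about 0.34. The ratio of mean to geometric difference is 1.07 at 0.5 and 1.21 at 0.7.

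**The case against.** The best defence is that the endpoint is defined by its method. Table 1 specifies the delta theorem applied to log-scale results, and 13.4.2 does not use the word arithmetic. A difference in geometric means is a sound summary for a skewed hormone, and it is more precise. In 4,000 simulated trials with 18 per arm, under the equal-variance assumptions above, its SD was 120 against 349 for the raw mean difference. Part of that gap is because the raw comparison was not adjusted for baseline. Section 13.3.4 also requires geometric means beside the arithmetic ones, so a careful reader could reconcile the two. SAP 10.5 leaves secondary endpoints without alpha control, and the final table in the example code prints the log-scale p-value. No decision rule depends on the ng/dL figure.

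Most of this stands, and it is why the remedy is relabelling rather than a different analysis. It does not rescue the wording. Naming a technique does not name a target, and where Appendix E does name one, it is a difference in means.

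A reader might go further and infer that the plan will understate the mean reduction. The documents do not support that without a condition. It follows from the common variance assumed in Appendix E, but nothing shows that variance will be equal across arms, and the working gives cases in both directions.

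**Conclusion.** The point holds as a mismatch between what 2.2 and 2.5 estimate and what the SAP says they estimate. They target a difference in geometric means. They are not consistent for the difference in arithmetic means, and the upward-bias rationale is wrong for that mean.

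The size cannot be fixed from the documents. Under log-normality and one log variance across arms, the reported figure falls short of the mean difference by a factor of 1.13 to 1.65 for log SDs of 0.5 to 1.0. With a larger drug-arm log variance it can exceed the mean difference. These figures illustrate the gap and do not measure it in this trial.

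A reader might also infer that the log-scale approach itself is faulty, or that the trial's main conclusion is at risk. Neither follows. The primary dose-response test and analyses 2.1, 2.3 and 2.4 do not use this step. What changes is the meaning of the ng/dL effect sizes.

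**What to change.** - In SAP 13.4.2, 13.4.5 and Appendix E, define 2.2 and 2.5 as differences in geometric means, in ng/dL at the geometric-mean baseline. State the covariate values at which the means are evaluated, because 13.4.5 replaces the log A4 covariate with the randomization stratum.
- Change the output labels and the 13.4.2 plot title to say geometric mean.
- Delete the claim of consistency for the mean and the claim that raw change gives upwardly biased means. Precision under skewness is a sufficient reason for the log scale.
- In the same edit, reconcile the appendix prose (e^(−L), plus twice the covariance) with the code (exp of the log mean, minus twice the covariance).

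The cost is wording and labels. No new data or model is needed.

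If an arithmetic mean difference in ng/dL is wanted, add a retransformed or smearing estimate as an optional supportive analysis. State its wider interval and its reliance on the variance assumption. An arm-specific correction is more than one extra term. The model in 13.3.2 has variance components common to all arms, and the correction must include baseline spread as well as residual variance. Arm-specific variances from about 15 subjects are also unstable. At an assumed log SD of 1.0 with 14 degrees of freedom, the 95% limits for σ² are 14/26.12 = 0.54 and 14/5.63 = 2.49, so exp(σ²/2) runs from about 1.3 to 3.5.

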#### **13.4.3 Third Secondary Efficacy Analysis**

The Third Secondary Efficacy analysis (see [Table 1](#), Analysis 2.3) is, in principal, identical to the Primary Efficacy Analysis except that now the dependent variable is 17-OHP.

To evaluate the dose response for change from baseline in log 17-OHP through 12 weeks of double blind randomized treatment, the analysis and presentation of results will be conducted in exact concordance with the Primary Efficacy Analysis of A4 levels as described in Section 13.3 with the only difference being the removal of log A4 as a covariate and the inclusion of the randomization stratification variable (study Week 4 A4 value [0 =  $A4 \leq 4 \times ULN$ ; 1 =  $A4 > 4 \times ULN$ ]) as a fixed factor effect.

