### 9.3.10 Baseline Values

Baseline values of serum biomarkers (i.e., A4, 17-OHP, and ACTH) are defined as the average of the Day 1, Week 4 and Week 6 assessments that are on or prior to the date of the first dose of double-blind study drug during Part A, allowing for unscheduled assessments to be windowed and replace missed scheduled visits. Visit windowing conventions will be used to identify the assessments that are used to construct baselines (see [Section 9.4](#)). Day 1 values are defined as the last non-missing assessment up to Day 14 for hormone assessments. For all other parameters, baseline values are defined as the last non-missing assessment prior to the first dose of randomized, double-blind study drug in Part A of the study. The following [Table 3](#) provides a guide for the baselines to use in analysis.

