## 10 STATISTICAL AND ANALYSIS ISSUES

### 10.1 Adjustments for Covariates

The categorical, randomization stratification variable (i.e., Week 4 A4 value [0 =  $A4 \leq 4 \times ULN$ ; 1 =  $A4 > 4 \times ULN$ ]) will be used in all efficacy analyses. The categorical variables treatment group (0 = placebo, 50 = 50 mg QD tildacerfont, 100 = 100 mg QD tildacerfont, and 200 = 200 mg QD tildacerfont) and sex (0=male, 1=female) will also be included efficacy analyses.

The log baseline serum A4, as a continuous covariate, will be included in a model for the analysis of change from baseline in A4 without the randomization stratification variable. The baseline GC dose, as a continuous covariate, will be included in models for the analysis of serum A4 and the change from baseline in GCs. The baseline value of continuous efficacy endpoints will be included in statistical models, such analysis of covariance (ANCOVA) or mixed-model for repeated measures (MMRM) as a continuous covariate for exploratory endpoints.

When fitting a logistic regression model, the treatment will be coded as 0 = placebo, 50 = 50 mg QD tildacerfont, 100 = 100 mg QD tildacerfont, and 200 = 200 mg QD tildacerfont. The treatment will be an explanatory variable in the model.

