### 13.5.8 Evaluation of ATCH

Exploratory Efficacy Analyses 3.12, 3.13 and 3.14 reflect the analysis of ATCH levels from baseline through 12 weeks of double blind randomized treatment. These Exploratory Efficacy Analyses will be achieved in exactly the same manner as Secondary Efficacy Analyses 2.3, 2.4 and 2.5 described in Sections 13.4.3, 13.4.4 and 13.4.5.

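### The 17-OHP secondary models (SAP 13.4.3 to 13.4.5) leave out baseline 17-OHP, so analyses 2.4 and 2.5 need not agree; and the Appendix E delta-method formula contradicts its own code

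*SAP*

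**What the plan says.** The primary A4 model (SAP 13.3.2) has log change from baseline as response and log baseline A4 among its covariates, with sex and baseline GC dose. For 17-OHP, SAP 13.4.3 (analysis 2.3), 13.4.4 (2.4) and 13.4.5 (2.5) each follow the matching A4 analysis "with the only difference being the removal of log A4 as a covariate and the inclusion of the randomization stratification variable". None of them names a baseline 17-OHP term.

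The general rule in SAP 10.1 does not fill the gap. It enters the endpoint's own baseline "as a continuous covariate for exploratory endpoints", and 2.3 to 2.5 are secondary. ACTH is exploratory, yet SAP 13.5.8 says of analyses 3.12 to 3.14: "These Exploratory Efficacy Analyses will be achieved in exactly the same manner as Secondary Efficacy Analyses 2.3, 2.4 and 2.5". They therefore inherit the same omission.

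Analysis 2.5 is run as in SAP 13.4.2, where the response becomes the log value instead of the log change, on the ground that "this re-run of the model with log A4 as the dependent variable will give precisely the same results, parameter estimates and variance-covariance matrix estimate". The absolute results are to be in concentration units: "The y-axis will be the CFB in ng/dL".

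Appendix E supplies the method. Its text lets the estimate "represent the estimated A4 CFB on the log scale", applies exp(-L), and adds twice the covariance in the variance of the between-arm difference. Its code fits "MODEL LPULSE = LBASE T G T*G / SOLUTION", exponentiates the log-level means with a positive sign, and subtracts twice the covariance.

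**The concern.** Log change equals log level minus log baseline. If log baseline is in the model, moving from change to level only raises that covariate's coefficient by 1, and every treatment contrast and its standard error is unchanged. If log baseline is absent, the two models differ by whatever baseline imbalance remains between arms after adjusting for the stratum. The equivalence claimed in SAP 13.4.2 is thus sound for A4 but does not carry over to 17-OHP as specified.

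At stake is the consistency of the 17-OHP results. The ratio-scale result (2.4) and the ng/dL result (2.5) would come from models the SAP treats as interchangeable, yet one could cross the nominal 5% level while the other does not. The Appendix E error is a separate matter: a programmer who follows the text rather than the code would report 2.2 and 2.5 with the wrong sign and without units.

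**Working it through.** **Inputs.** The plan gives no figure for 17-OHP. Its sample-size paragraph concerns A4 and supplies only the arm size, 15/0.85 = 17.6, rounded up to 18. Hormone baselines "are defined as the average of the Day 1, Week 4 and Week 6 assessments" (SAP 9.3.10). Assumed, because the documents do not state them: correlation r between averaged baseline and Week 18 log 17-OHP of 0.3 to 0.8; correlation c = 0.7 between log A4 and baseline log 17-OHP; a stratum splitting A4 at its median; equal correlation ρ between visits.

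**Precision.** Per unit log variance, the averaged baseline has variance v = (1 + 2ρ)/3, and r = ρ/√v. A median split correlates √(2/π) = 0.798 with the underlying normal variable. Take the stratum as independent of Week 18 given baseline. The residual variances are:
- own baseline in the model: 1 - r²
- level with stratum only (2.5): 1 - (0.798·c·r)²
- change with stratum only (2.4): 1 + v - 2ρ - (0.798·c·r - 0.798·c·√v)²

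At r = 0.7: ρ = 0.599, v = 0.733, √v = 0.856.
- Own baseline: 0.510.
- Level: 1 - 0.391² = 0.847; SE ratio √(0.847/0.510) = 1.289.
- Change: 1 + 0.733 - 1.198 - (0.391 - 0.478)² = 0.527; SE ratio √(0.527/0.510) = 1.016.

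| r | ρ | Own baseline | Level (2.5) | Change (2.4) | SE ratio 2.5 | SE ratio 2.4 |
|---|---|---|---|---|---|---|
| 0.3 | 0.206 | 0.910 | 0.972 | 1.012 | 1.033 | 1.055 |
| 0.5 | 0.384 | 0.750 | 0.922 | 0.799 | 1.109 | 1.032 |
| 0.7 | 0.599 | 0.510 | 0.847 | 0.527 | 1.289 | 1.016 |
| 0.8 | 0.722 | 0.360 | 0.800 | 0.367 | 1.491 | 1.010 |

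With c varied from 0.5 to 0.9, the loss in 2.5 is 2-4%, 8-13%, 21-35% and 36-58% at the four values of r.

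**Size of the 2.4 versus 2.5 gap.** On the log scale the two effects differ by the stratum-adjusted baseline imbalance. Its variance is v(1 - (0.798c)²)·2/18 times the log variance. At r = 0.3 and log SD 1.0 this is 0.471 × 0.688 × 2/18 = 0.0360, SD 0.190. In 5% of trials the effects then differ by more than exp(1.96 × 0.190) = 1.45-fold. In simulation the figures for r = 0.3 to 0.8 are 1.45- to 1.64-fold at log SD 1.0 and 1.21- to 1.28-fold at log SD 0.5.

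**Disagreement on significance.** Simulation with 10,000 trials per setting, four arms of 18, a true 50% reduction at Week 18 and one drug-placebo contrast; the 2.4 p-value is compared with the 2.5 absolute-scale confidence interval:

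| Log SD | As written (r = 0.3/0.5/0.7/0.8) | Own baseline added |
|---|---|---|
| 1.0 | 20% / 24% / 33% / 39% | 8% / 6% / 3% / 1% |
| 0.75 | 15% / 15% / 16% / 16% | 3% / 2% / 0.4% / 0.1% |
| 0.5 | 1.8% / 1.4% / 0.7% / 0.5% | 0.1% or less |

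The mean 2.5 ratio was 0.498 to 0.503 against a true 0.50, so there is no bias. The simulation used Week 18 only and omitted sex and GC dose, which could reduce the loss.

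**Repeated-measures check.** One simulated trial (Weeks 4, 8 and 12 of treatment, quadratic time by arm, random intercept only, sex and GC dose included) gave -0.5059 (SE 0.2299) for both level and change with own baseline. With the stratum only it gave -0.472 (SE 0.293) for level and -0.423 (SE 0.244) for change. The treatment-by-time likelihood-ratio statistic was 9.87 in all four fits, so the test in 2.3 is essentially untouched.

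**Appendix E.**
- Drug L = ln 0.5, placebo L = 0. Text: exp(-L) gives 2 - 1 = +1.0. With exp(L): 0.5 - 1 = -0.5. Both are ratios, not ng/dL.
- Geometric means 600 and 1000 ng/dL on the log level. Code: 600 - 1000 = -400 ng/dL. Text: 1/600 - 1/1000 = +0.00067.
- Variance with illustrative log-scale SE 0.2 per arm and covariance 0.01: 120² + 200² - 2(0.01)(600)(1000) = 42,400, SE 206. With the plus sign: 66,400, SE 258. A separate Monte Carlo run gave 1525, matching the minus sign (1520) and not the plus sign (3920).
- The code passes covariance column 7 for all three visits, which can match the placebo mean at only one of them.

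**The case against.** **The intention may be correct.** SAP 13.4.3 describes the 17-OHP analysis as identical in principle to the primary, Protocol 9.4.3.1 calls for the primary's methodology, and the Appendix E template carries own baseline in both models. A programmer might well substitute baseline 17-OHP. That is plausible, but the wording, used three times, admits no other difference; SAP Section 4 makes the SAP govern; and Section 15 lists no such departure.

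**The equivalence sentence concerns A4 only.** True. It reaches 17-OHP because 13.4.5 requires exact concordance with 13.4.2, so this is an inference from two sections.

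**The ACTH conflict is arguable**, because SAP 10.1 gives ANCOVA and MMRM as its examples, not the random-coefficients model. That is fair; the sections still need reconciling.

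**The size rests on assumptions.** This stands. Disagreement runs from 0.5% to 39%, and some remains at log SD 1.0 even with own baseline, because a delta-method interval is compared with a log-scale p-value. At r = 0.3, 2.4 loses more precision than 2.5.

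**Disagreement means crossing 0.05, not opposite directions.** Also right: opposite signs occurred in at most 2% of simulated trials in any setting. SAP 13.4.2 asks for an interval rather than a p-value, and SAP 10.5 makes these endpoints nominal.

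**Appendix E is editorial**, since the code has the right transform and covariance sign and a positive, unitless result would be noticed. That limits the likely harm, but the stated formula is still wrong.

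**Conclusion.** Both parts hold.

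As written, no 17-OHP secondary model adjusts for baseline 17-OHP. Analyses 2.3 and 2.4 remain valid log-change analyses, with a standard-error loss of 1.0% to 5.5%. Analysis 2.5 is unbiased under randomization but carries chance baseline imbalance, costs 3% to 49% in standard error over r = 0.3 to 0.8, and is not the equivalent of 2.4 that the SAP supposes. The practical effect is negligible if the log SD is near 0.5 and material at 0.75 to 1.0. Confidence is high in the textual defect; its size depends on a variance and correlations the documents do not give.

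The Appendix E text is wrong whatever those values are, and it bears on 2.2 as well as 2.5. The primary A4 analysis is not affected.

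**What to change.** - In SAP 13.4.3 to 13.4.5, add log baseline 17-OHP as a continuous covariate, keeping the Week 4 A4 stratum if wanted. In 13.5.8, add log baseline ACTH likewise. Analyses 2.4 and 2.5 then rest on equivalent models and 13.5.8 agrees with 10.1.
- In the Appendix E text, define L as the estimated mean log level at the visit, use exp(L), change the covariance term to -2Cov, and label the result a difference in geometric means in ng/dL. State also how each arm's change from baseline in ng/dL is formed for the plot in 13.4.2.
- When the three-group example code is adapted to four arms, take the covariance with placebo at the same visit rather than one fixed column.

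The cost is SAP wording and one covariate per hormone that is already collected. No new data are needed, and the change can be made before unblinding.
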